### **9.1.6 Posttreatment Telemedicine Visit(s)**

In subjects who consent to the posttreatment Telemedicine Visit(s), current status of symptoms from resolved or ongoing AEs of rash will be discussed via a telephone or video interview, which may consist of multiple telemedicine visits, if necessary according to AE resolution status.

This telemedicine visit will be 6 months after last dose or AE of rash resolution as follows:

- subjects with no AEs of rash are to be followed for up to 6 months after the last dose of study drug
- subjects with AEs of rash are to be followed for up to 6 months following resolution of their respective AE(s) of rash

Recommended precautions for exposure to sunlight (Section 9.4.1) should be followed through the final posttreatment Telemedicine Visit. Subjects should also be instructed to contact the investigational site if they develop new or worsening rash.

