Study Duration	Excluding the Screening Period, each subject will participate in the study for approximately 52 weeks (48-week Treatment Period and 28-day Safety Follow-up Period). In subjects who consent to the posttreatment Telemedicine Visit(s), the total duration for study participation will increase by approximately 24 weeks (i.e., approximately 76 weeks total, from Screening Period through posttreatment Telemedicine Visit).
Study Design	This is a Phase 2, open-label, multicenter study. Approximately 20 subjects with the PiZZ genotype will be enrolled. Groups A and B will enroll approximately 10 subjects each. All subjects will receive VX-864 500 mg every 12 hours (q12h) for 48 weeks. Figure 2-1 displays the study design. Group A subjects will not have a liver biopsy. Subjects in Group B will have 2 liver biopsies performed over the course of the study. All liver biopsies will be performed percutaneously. All subjects in Group B (approximately 10 subjects) will have a liver biopsy during the Pretreatment Interval (Figure 2-1). Approximately 5 subjects (Cohort B1) will have a second liver biopsy at Week 24. Approximately 5 subjects (Cohort B2) will have a second liver biopsy at Week 48. The pretreatment liver biopsy must be performed at least 7 days before Day 1 dosing, after all eligibility criteria have been met. Local laboratory hematology and coagulation results must be collected and reviewed by investigator within approximately 48 hours prior to the liver biopsy being performed. The Week 24 and Week 48 liver biopsies will be performed 3 hours ( $\pm$ 30 minutes) postdose relative to the morning dose. The Safety Follow-up Visits are required for all subjects. In subjects who terminate their participation early, the ETT visit, which may be conducted at the site or by telephone or video interview, replaces the Safety Follow-up Visit, if the

ETT Visit occurs 3 weeks or later following the last dose of study drug. All subjects may also consent to the posttreatment Telemedicine Visit(s) following final dose of study drug, to monitor for development of AEs of rash (for up to 6 months) and to monitor any ongoing AEs of rash (for up to 6 months following resolution of AEs of rash; see Section 9.1.6).

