## **9                   STUDY IMPLEMENTATION**

### **9.1               Study Design**

This is a Phase 2, open-label, multicenter study. A schematic of the study design is shown in Figure 9-1. Approximately 20 subjects with the PiZZ genotype will be enrolled. Groups A and B will enroll approximately 10 subjects each. All subjects will receive VX-864 500 mg every 12 hours (q12h) for 48 weeks. Group A subjects will not have a liver biopsy. Subjects in Group B will have 2 liver biopsies performed over the course of the study. All liver biopsies will be performed percutaneously. All subjects in Group B (approximately 10 subjects) will have a liver biopsy during the Pretreatment Interval (Figure 9-1). Approximately 5 subjects (Cohort B1) will have a second liver biopsy at Week 24. Approximately 5 subjects (Cohort B2) will have a second liver biopsy at Week 48. The pretreatment liver biopsy must be performed at least 7 days before Day 1 dosing, after all eligibility criteria have been met. Local laboratory hematology and coagulation results must be collected and reviewed by investigator within approximately 48 hours prior to the liver biopsy being performed. The Week 24 and Week 48 liver biopsies will be performed 3 hours ( $\pm$ 30 minutes) postdose relative to the morning dose. The Safety Follow-up Visits are required for all subjects. In subjects who terminate their participation early, the ETT visit, which may be conducted at the site or by telephone or video interview, replaces the Safety Follow-up Visits, if the ETT Visit occurs 3 weeks or later following the last dose of study drug. All subjects may also consent to the posttreatment Telemedicine Visit(s) following final dose of study drug, to monitor for development of AEs of rash (for up to 6 months) and monitor any ongoing AEs of rash (for up to 6 months following resolution of AEs of rash; see Section 9.1.6).

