### **9.1.4        Safety Follow-up**

The Safety Follow-up Visits are scheduled to occur 14 and 28 ( $\pm$  2) days after the last dose of study drug. The Safety Follow-up Visit assessments are listed in Table 3-4.

The Safety Follow-up Visits are required for all subjects.

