### **9.1.9 Completion of Study Participation**

Completion of study participation for each individual subject is defined as one of the following:

- For subjects who complete the Treatment Period: the last Safety Follow-up Visit.
- For subjects who prematurely discontinue study drug treatment but do not withdraw consent, the latest of the following: the Week 48 Visit, ETT Visit, or the last Safety Follow-up Visit (if required), or the last posttreatment Telemedicine Visit.
- For subjects who withdraw consent: the date of withdrawal of consent (Section 9.9).

If subjects are lost to follow-up (Section 9.1.8), the date of completion of study participation will be defined as the date of last contact.

The end of study is defined in Section 13.2.9.

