7.1 Overall Design

This is a Phase 2, open-label, multicenter study. Approximately 20 subjects with the PiZZ genotype will be enrolled. Groups A and B will enroll approximately 10 subjects each. All subjects will receive VX-864 500 mg every 12 hours (q12h) for 48 weeks. Figure 7-1 displays the study design.

Group A subjects will not have a liver biopsy.

Subjects in Group B will have 2 liver biopsies performed over the course of the study. All liver biopsies will be performed percutaneously. All subjects in Group B (approximately 10 subjects) will have a liver biopsy during the Pretreatment Interval (Figure 7-1). Approximately 5 subjects (Group B1) will have a second liver biopsy at Week 24. Approximately 5 subjects (Group B2) will have a second liver biopsy at Week 48.

The pretreatment liver biopsy must be performed at least 7 days before Day 1 dosing, after all eligibility criteria have been met. Local laboratory hematology and coagulation results must be collected and reviewed by investigator within approximately 48 hours prior to the liver biopsy being performed. The Week 24 and Week 48 liver biopsies will be performed 3 hours (± 30 minutes) postdose relative to the morning dose.

The Safety Follow-up Visits are required for all subjects. For subjects who terminate their participation early, the ETT visit, which may be conducted at the site or by telephone or video interview, replaces the Day 28 Safety Follow-up Visit, if the ETT Visit occurs 3 weeks or later following the last dose of study drug. All subjects may also consent to the posttreatment Telemedicine Visit(s) following final dose of study drug, to monitor for development of AEs of rash (for up to 6 months) and to monitor any ongoing AEs of rash (for up to 6 months following resolution of AEs of rash; see Protocol Section 9.1.6).

Figure 7-1 VX22-864-108 Study Design

Treatment Period		
Day 1 to Week 48, VX-864 (N=20)		
Screening Up to 70 days before first dose ^a	Group A (n=10) No liver biopsy	Safety Follow-up 14 and 28 (± 2) days after last dose, and posttreatment telemedicine visit(s) ^c
Group B Pretreatment Interval Up to 14 days ^b before first dose	Cohort B1 (n=5) Liver biopsy at Pretreatment Interval and Week 24	
	Cohort B2 (n=5) Liver biopsy at Pretreatment Interval and Week 48	

[figure not shown]
n: size of subsample; N: number of subjects

Notes: Figure is not drawn to scale. Figure is not drawn to scale.

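### Protocol 9.1.6 counts posttreatment rash follow-up from rash resolution alone for anyone with a rash AE; elsewhere all consenting subjects keep a window of up to 6 months after the last dose

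*Protocol*

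**What the plan says.** Section 9.1.6 of the protocol describes an optional telephone or video contact for subjects who consent to it. The lead-in on timing is "This telemedicine visit will be 6 months after last dose or AE of rash resolution as follows". Two bullets follow, each with one clock. The first, for subjects without a rash AE, counts from the last dose. The second counts from resolution instead: "subjects with AEs of rash are to be followed for up to 6 months following resolution of their respective AE(s) of rash". The opening sentence of the section makes clear that resolved rash is in scope as well as ongoing rash.

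Section 9.1 gives the purpose differently: "All subjects may also consent to the posttreatment Telemedicine Visit(s) following final dose of study drug, to monitor for development of AEs of rash". The limit it sets on this monitoring is 6 months. It then adds a second purpose, the monitoring of rash that is still ongoing. The same pair of purposes stands in the Synopsis, in the footnotes to Figures 2-1 and 9-1 and Tables 3-3 and 3-4, and in SAP 7.1. The SAP states the second purpose as "to monitor any ongoing AEs of rash (for up to 6 months following resolution of AEs of rash; see Protocol Section 9.1.6". All of these places send the reader to 9.1.6 for the detail.

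Sections 9.1.6 and 9.4.1 keep sun precautions in force until the final telemedicine visit. The Synopsis puts participation for consenting subjects at "approximately 76 weeks total, from Screening Period through posttreatment Telemedicine Visit".

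**The concern.** The two descriptions differ for one kind of subject: someone whose rash began and cleared while on drug. Section 9.1 and the places that match it keep that subject under watch for new rash after the final dose, like everyone else who consents. The second bullet of 9.1.6 moves the same subject to a clock that began at resolution, before dosing ended.

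Safety is a secondary objective, and detecting new rash after dosing is a stated purpose of this visit. With screening, enrollment and dosing over, rash follow-up is one of the few protocol activities still to be carried out. A site that applied the bullet as written would watch subjects who had already shown a rash for less time after the last dose than subjects who had not. It could release them from sun precautions sooner too.

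**Working it through.** **1. The plan's own figure.** Synopsis, Study Duration: 48 weeks of treatment + 4 weeks (28 days) of safety follow-up = 52 weeks. Adding about 24 weeks for telemedicine gives 52 + 24 = 76 weeks, as stated. One total is given for all consenting subjects.

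**2. The two rules side by side** (latest follow-up date; L = last dose, R = rash resolution)

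| Subject | Section 9.1.6 bullets | Section 9.1, Synopsis, footnotes, SAP 7.1 |
|---|---|---|
| No rash AE | L + 6 months | L + 6 months |
| Rash resolves on or after the last dose | R + 6 months | R + 6 months for that rash, with L + 6 months for new rash inside it |
| Rash resolved before the last dose | R + 6 months | L + 6 months for new rash; nothing is ongoing |

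The rules agree in the first two rows and part in the third.

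**3. Size of the difference.** Let g = L − R, in weeks, for a rash that resolved before the last dose.

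- Limit under the second bullet: R + 6 months = L + 6 months − g.
- Limit for a rash-free subject: L + 6 months.
- Difference: (L + 6 months) − (L + 6 months − g) = g weeks.

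An illustration, with g = 12 weeks assumed and 6 months taken as 24 to 26 weeks: the limit falls 24 − 12 = 12 to 26 − 12 = 14 weeks after the last dose, against 24 to 26 weeks for a rash-free subject. If a rash instead resolves 8 weeks after the last dose, the limit is 24 + 8 = 32 to 26 + 8 = 34 weeks after it under either rule.

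**4. What is known about g.** It cannot exceed the subject's time on drug. Protocol 9.3.2 and 9.6.1 record that dosing stopped as of 25 September 2023. Neither document gives individual exposure or a count of rashes that resolved on treatment. SAP 9.3.2 reports that no subject had a post-treatment liver biopsy; the earliest was scheduled for Week 24, in Cohort B1. That suggests shorter exposure in Group B at least, without proving it. So neither g nor the number of affected subjects can be estimated.

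**5. Reach into the analysis.** The treatment-emergent period ends no later than 28 days after the last dose (Protocol 12.3.1, SAP 9.1), and the AE summary tables cover treatment-emergent events only (SAP 9.4.1). A shift in a call due around 6 months changes none of them, and no efficacy endpoint depends on it.

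**The case against.** The strongest reply is that the protocol read as a whole already settles the matter. The schedule footnotes, which sites use to book visits, give every consenting subject the window after the final dose. The visit is called posttreatment, and the lead-in to 9.1.6 names both dates. On that reading the second bullet extends follow-up for subjects with rash and takes nothing away. This is probably what was intended. It stands as evidence of intent, but not as a rule: the bullets give each subject one date, and the other sections defer to them. Those sections do not contain the words *whichever is later* either. The mismatch lies in their covering all subjects for new rash and in their restriction of the resolution clock to ongoing rash.

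Section 9.1.9 does have a latest-date rule, "the latest of the following: the Week 48 Visit, ETT Visit, or the last Safety Follow-up Visit (if required", in a list that goes on to the last telemedicine visit. It defines completion of participation for subjects who stop treatment early; it does not set the date of the call.

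Several safeguards also stand. The visit is optional and 6 months is an upper limit. "The Safety Follow-up Visits are required for all subjects", at 14 and 28 days after the last dose, unless an ETT Visit replaces them (9.1.5). Subjects are told to contact the site about new or worsening rash, and each AE is followed to a final outcome (13.1.1.7). These keep the point small.

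Two stronger readings are tempting:

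- **That the call disappears.** A reader might infer that a rash resolved about 26 weeks or more before the last dose leaves no call after dosing. That needs at least that much time on drug, which the documents do not show for any subject. It also needs a site to date a posttreatment visit during treatment, against its title and Section 9.1.
- **That the 76-week total promises each consenting subject a fixed length of follow-up after dosing.** It is an approximate duration built on a full 48-week course, which the dosing stop overtook. It cannot hold for a rash that resolves well after the last dose, so it does not show which timing rule was meant.

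**Conclusion.** The inconsistency is real and minor. Taken literally, the second bullet of 9.1.6 lets the final optional call, and the end of sun precautions, fall up to g weeks earlier after dosing for a subject whose rash resolved g weeks before the last dose. This rests on the bullet being applied as written and on at least one consenting subject having had a rash that cleared on drug. The documents confirm neither, so the effect in practice may be small or zero. The safety tables and efficacy results are untouched. Correcting the wording is worthwhile because it is cheap and the follow-up it governs is still active, but it is optional.

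**What to change.** Amend the second bullet of Protocol 9.1.6 so that subjects with a rash AE are followed for up to 6 months after the last dose or up to 6 months after their rash resolves, *whichever is later*. Add the same three words to the lead-in sentence. This brings 9.1.6 into line with Section 9.1, the Synopsis, the footnotes and SAP 7.1, none of which needs to change.

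The cost is a later optional telephone or video call and longer sun precautions for a few consenting subjects. No clinic visit, procedure or analysis is added.

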### **9.1.7 Timing Under Extenuating Circumstances**

In the event that extenuating circumstances (e.g., events related to COVID-19) or unforeseen conditions (e.g., natural disasters or unforeseen external factors impacting clinical site) alter the timing of a scheduled visit being conducted, the investigator should notify the medical monitor, and the visit window specified in the Schedule of Assessments during the Treatment Period may be expanded by up to  $\pm$  7 days upon consultation with the investigator and medical monitor.

For study visits requiring a liver biopsy, the visit will be rescheduled upon consultation with the investigator and medical monitor.

### **9.1.8 Lost to Follow-up**

A subject will be considered lost to follow-up if both of the following occur:

- The subject misses 2 consecutive study visits (telephone contact, clinic, and/or home visit) and is subsequently unable to be contacted by telephone (3 documented attempts by telephone within 2 weeks following the second missed visit)
- The subject does not respond within 2 weeks to a registered letter sent after the 3 attempted telephone contacts.

### **9.1.9 Completion of Study Participation**

Completion of study participation for each individual subject is defined as one of the following:

- For subjects who complete the Treatment Period: the last Safety Follow-up Visit.
- For subjects who prematurely discontinue study drug treatment but do not withdraw consent, the latest of the following: the Week 48 Visit, ETT Visit, or the last Safety Follow-up Visit (if required), or the last posttreatment Telemedicine Visit.
- For subjects who withdraw consent: the date of withdrawal of consent (Section 9.9).

If subjects are lost to follow-up (Section 9.1.8), the date of completion of study participation will be defined as the date of last contact.

The end of study is defined in Section 13.2.9.

## 9.2 Method of Assigning Subjects to Treatment Groups

This is an open-label study.

## 9.3 Rationale for Study Elements

### 9.3.1 Study Population

This Phase 2 study will enroll consented subjects who meet the eligibility criteria. Results from this study will provide information on the efficacy, safety, tolerability, [REDACTED] of the orally administered VX-864 in male and female subjects with AATD who are aged 18 to 80 years, inclusive (Group A), and aged 18 to 70 years, inclusive (Group B), and have the PiZZ genotype.

### 9.3.2 Study Drug Dose and Duration

Up to the time of dosing suspension, subjects received VX-864 q12h for 48 weeks. The dose of VX-864 was 500mg q12h. As of 25 September 2023 all dosing has been suspended.

### 9.3.3 Rationale for Study Assessments

All safety assessments are standard parameters for clinical studies in drug development. The efficacy parameters being evaluated are widely accepted and generally recognized as reliable, accurate, and relevant to the study of individuals with AATD. Similar parameters were measured in Phase 1 and Phase 2 studies of VX-864 in healthy subjects and in subjects with AATD who have the PiZZ genotype.

Blood samples will be collected to evaluate the effect of VX-864 on blood levels of functional AAT, antigenic AAT, and Z-polymer, and based on the mechanism of action of VX-864 and its anticipated effect in this population.

A key histologic change in AATD-related hepatic disease is Z-polymer accumulation in the liver (Group B subjects only). [REDACTED]

## 9.4 Study Restrictions

Study restrictions are summarized in Table 9-1. A non-exhaustive list of study prohibitions and cautions for medication will be provided in the Study Reference Manual.

**Table 9-1 Study Restrictions**

Restricted Medication/Food/Activity a	Timing of Restriction	
	Start	Stop
Depo-Provera®	6 months before first dose of study drug	28 days after final dose of study drug
Hormonal methods of contraception (oral or patch)	28 days before first dose of study drug	28 days after final dose of study drug
Sensitive CYP3A substrates except inhaled and topical formulations b, c	7 days or 5 half-lives (whichever is longer) before the first dose of study drug	28 days after final dose of study drug

**Table 9-1 Study Restrictions**

Restricted Medication/Food/Activity a	Timing of Restriction	
	Start	Stop
UGT1A1/UGT1A4 moderate and strong inhibitors	7 days or 5 half-lives (whichever is longer) before the first dose of study drug	28 days after final dose of study drug
UGT1A1/UGT1A4 moderate and strong inducers	14 days before the first dose of study drug	
Prescription or nonprescription NSAIDs, anti-coagulants, or anti-platelet agents (e.g., warfarin, clopidogrel, aspirin, ibuprofen)	10 days before liver biopsy c	28 days after final dose of study drug
Other investigational drugs or devices	28 days before screening, 5 half-lives before screening, or time determined by local requirements (whichever is longer)	28 days after final dose of study drug
Augmentation therapy (human alpha-1 proteinase inhibitor)	More than 42 days before level of antigenic AAT is obtained for eligibility	28 days after final dose of study drug
Tobacco products, including use of electronic tobacco devices, e.g., e-cigarettes d	6 months before screening	28 days after final dose of study drug
Inhaled cannabis	6 months before screening	28 days after final dose of study drug
Alcohol: no more than 1 drink/day for females or 2 drinks/day for males (1 drink = 5 ounces [150 mL] of wine or 12 ounces [360 mL] of beer or 1.5 ounces [45 mL] of hard liquor)	Signing of ICF	28 days after final dose of study drug

AAT: alpha-1 antitrypsin; ICF: informed consent form; NSAID: nonsteroidal anti-inflammatory drug;

UGT1A1/A4: uridine diphosphate glucuronosyltransferase family 1 member A1/A4

a See Section 9.5 for guidance on concomitant medications.

b Chronic use of corticosteroids is prohibited with the exception that subjects may receive doses of prednisone or prednisolone of up to 5 mg/day chronically. Use of rosuvastatin at doses of up to 10 mg/day, and atorvastatin at doses of up to 20 mg/day is permitted. Also, an acute course of corticosteroids (as described in Section 9.5) as standard of care to treat a pulmonary exacerbation is permitted (dose and duration per investigator judgment in consultation with the Sponsor). In addition, use of inhaled fluticasone propionate and inhaled salmeterol are prohibited.

c In Group B only, sedation and local anesthesia (e.g., midazolam, fentanyl, local lidocaine) used for the liver biopsy procedure are allowed. Low-dose non-NSAID pain medications (e.g., acetaminophen with codeine, oxycodone, acetaminophen with oxycodone) are allowed for post-procedure pain. VX-864 may cause increased exposure of sensitive CYP3A4 substrates. When utilizing sensitive CYP3A4 substrates for sedation, local anesthesia, or acute pain management, caution should be utilized and dose adjustments may be considered.

d Nicotine replacement therapy under the direction of a physician is allowed.

e During the Treatment Period, occasional, limited ibuprofen ( $\leq 1200$  mg/day) use for pain is allowed in both Groups A and B. In Group B only, limited ibuprofen use for pain is allowed until 10 days before the liver biopsy, at which time all ibuprofen use is prohibited until 2 weeks after the liver biopsy.

